17.5. VITAL SIGNS

The following Vital Signs measurements will be reported at each visit:

- Systolic Blood Pressure (mmHg)
- Diastolic Blood Pressure (mmHg)
- Pulse Rate (bpm)
- Respiratory Rate (breaths/min)
- Temperature (°C)

If clinically significant findings, as determined by the Investigator, occur in any of the vital signs measurements, that measurement will be repeated at medically appropriate intervals until the value returns to an acceptable range, a specific diagnosis is established, or the condition is otherwise explained.

Document: C:\Users\q832483\Documents\Insy CSR\Pending\Ready for QC\New folder\Statistical Analysis Plan.docx
Author: [REDACTED] Version Number: V1.0 Final
Version Date: 04APR2017

Template No: CS_TP_BS016 – Revision 3
Effective Date: 01May2012

Reference: CS_WI_BS005

The following summaries will be provided for vital signs data:

- Actual and change from baseline by time point and age category
- Incidence of markedly abnormal values
- All vital signs will be listed

Each vital sign result will be compared to the both baselines as defined [Section 6.2](#).

Each vital sign result measured at the Follow-up visit will also be summarized (as described above) by CBD status.

In addition, the subject weight will be summarized in terms of both:

- Change from baseline across each visit
- Change from baseline to Follow-up visit by CBD status

The corresponding listing will also be provided including the flag for CBD status.

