17.5.1. VITAL SIGNS MARKEDLY ABNORMAL CRITERIA

Markedly abnormal quantitative Vital Signs measurements will be identified in accordance with the following predefined markedly abnormal criteria:

Variable	Unit	Low	High
SBP	mmHg	≤ 90 mmHg AND change from baseline ≤ -20 mmHg	≥ 180 mmHg AND change from baseline ≥ 20 mmHg
DBP	mmHg	≤ 50 mmHg AND change from ≤ -15 mmHg	≥ 105 mmHg AND change from baseline ≥ 15 mmHg
Heart rate	Bpm	≤ 50 bpm AND change from baseline ≤ -15 bpm	≥ 120 bpm AND change from baseline ≥ 15 bpm
Body temperature	°C	NA	≥ 38.3 °C AND change from baseline ≥ 1.1 °C

Respiratory rate will be classified as Low and High according to the following age-dependent ranges (Low for values under the range and High for values above the range):

Age Category	Normal Respiratory Rate Range (Breaths Per Minute)
< 3 years	20-30 bpm
3 -< 6 years	20-25 bpm

Document: C:\Users\q832483\Documents\Insy CSR\Pending\Ready for QC\New folder\Statistical Analysis Plan.docx
Author: [REDACTED] Version Number: V1.0 Final
Version Date: 04APR2017

Template No: CS_TP_BS016 – Revision 3
Effective Date: 01May2012

Reference: CS_WI_BS005

6 < 12 years	14-22 bpm
≥ 12 years	12-18 bpm

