APPENDIX 2. ADVERSE EVENTS OF SPECIAL INTEREST PREFERRED TERMS

- Anemia;
- Diarrhea;
- Fatigue;
- Blood FSH decreased;
- Blood FSH increased;
- Weight decreased;
- Weight increased;
- Decreased appetite;
- Hypersomnia;
- Lethargy;
- Sedation;
- Seizure;
- Somnolence;
- Status epilepticus;
- Aggression;
- Agitation;
- Irritability;
- Acute respiratory failure;
- Dyspnea;
- Respiratory arrest.

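### Respiratory rate is the only vital sign SAP 17.5.1 flags on a normal range alone, so the markedly abnormal count would mix long-standing out-of-range values with new ones

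*SAP*

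**What the plan says.** SAP 17.5.1 opens with "Markedly abnormal quantitative Vital Signs measurements will be identified in accordance with the following predefined markedly abnormal criteria". A table then covers systolic and diastolic pressure, heart rate and temperature. Every criterion in it joins an absolute limit to a change; low systolic pressure, for example, is "≤ 90 mmHg AND change from baseline ≤ -20 mmHg".

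Respiratory rate follows below that table, in the same section, under a different rule: "Respiratory rate will be classified as Low and High according to the following age-dependent ranges". Anything below the band counts as Low and anything above it as High. The ranges are headed as normal ranges: 20-30 under 3 years, 20-25 from 3 to under 6, 14-22 from 6 to under 12, and 12-18 from 12 years. The rule has no extreme limit and no change condition.

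SAP 17.5 states "The following Vital Signs measurements will be reported at each visit" and names respiratory rate among them. It plans actual values and changes by time point and age category, "Incidence of markedly abnormal values", and a full listing. It compares each result with both baselines of SAP 6.2 and repeats the summaries by CBD status at follow-up. It plans no shift table for vital signs.

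**The concern.** Under one heading the SAP applies two different kinds of rule. Four vital signs are flagged for a marked and new departure. The fifth is flagged for any value one breath outside a normal range, whatever the child's own baseline.

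The study is open-label with no comparator, so a child's own baseline is the main reference for reading a flag. An incidence that ignores baseline cannot tell a new finding from an old one. A reader who sets the respiratory rate row beside the blood pressure row would be comparing unlike things.

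Respiratory events matter in this study. Appendix 2 lists "Acute respiratory failure", dyspnea and respiratory arrest as adverse events of special interest. A high flag count that came mainly from ordinary variation could cause false concern, or teach readers to disregard the row.

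**Working it through.** **1. Same situation, two rules.** Take a child aged 4 with a respiratory rate of 26 at baseline and at every later visit. The change is 0, the range is 20-25, and the child is High each time. Take another child with systolic pressure 88 at baseline and throughout. The value meets the absolute limit of 90, but the change of 0 does not reach -20, so the child is never flagged.

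**2. Does Low/High feed the incidence table?** The SAP text does not say so outright. The rule sits in the markedly abnormal section. Of the three vital-sign outputs in SAP 17.5, the incidence count is the only summary that could use a Low/High class, since the others are numerical summaries and a listing. The natural reading is yes.

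**3. The SAP's own laboratory practice.** SAP 17.3 puts Low/Normal/High into shifts from baseline. SAP 17.3.1 defines markedly abnormal liver tests as a separate, additional rule (above 3 times ULN for ALT and AST, above 2 times for total bilirubin). Respiratory rate merges the two ideas.

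**4. How many children?** The plan states no expected flag rate, so there is no figure to reproduce. As illustration only:

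- From the documents: the four ranges, and nine scheduled visits after Day 1 (Visits 3 to 11, Protocol Table 1).
- Assumed: normal distribution, whole-number recording, mean at the range midpoint, SD 2 or 3 breaths/min, within-child correlation 0.5 or 0.8, and no drug effect.

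With h = (U - L)/2 + 0.5, the per-visit probability is p = 2[1 - Φ(h/SD)]. For ages 3 to under 6, h = 5/2 + 0.5 = 3, so at SD 3, p = 2[1 - Φ(1)] = 31.7%. If visits were independent, the share ever flagged would be 1 - (1 - 0.317)^9 = 96.8%. Correlated visits were simulated with 50,000 children.

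| Age (years) | h | Per visit, SD 2 | Per visit, SD 3 | Ever, SD 2, corr. 0.5 | Ever, SD 3, corr. 0.5 | Ever, SD 3, corr. 0.8 |
|---|---|---|---|---|---|---|
| <3 | 5.5 | 0.6% | 6.7% | 4% | 34% | 21% |
| 3 to <6 | 3.0 | 13.4% | 31.7% | 57% | 91% | 71% |
| 6 to <12 | 4.5 | 2.4% | 13.4% | 15% | 57% | 37% |
| ≥12 | 3.5 | 8.0% | 24.3% | 40% | 82% | 59% |

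For half of all visits to be flagged, the SD would have to be 8.2, 4.5, 6.7 and 5.2 in the four bands. With the mean 2 breaths above the midpoint, SD 3 and correlation 0.5, the ever-flagged shares are 48%, 94%, 68% and 87%.

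Nine visits is the scheduled maximum. Up to 20 of the 80 subjects come from INS011-15-054, with a discretionary entry visit and a capped combined duration (Protocol 3.1 and 3.4).

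**5. Which age assigns the band?** SAP 17.5.1 does not say. SAP 7.4 uses age at the start of the previous study for display, and SAP 10.1 uses age at consent. The choice matters: an unchanged rate of 24 is Normal at age 5 and High at 6, and 20 is Normal at 11 and High at 12.

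**The case against.** The strongest reply is that this is one descriptive flag among several safety outputs. SAP 17.5 already summarises respiratory rate and its change from both baselines, by visit and age category, and lists every value. Protocol 6.1.5 makes a clinically significant vital-sign finding an adverse event unless it fits a current diagnosis. SAP 17.1.6 tabulates the respiratory events of special interest. In a single-arm study no flag count isolates a drug effect in any case. The wording for respiratory rate also reads like an ordinary Low/Normal/High class, and the table templates mentioned in SAP 8, which are not among the documents, may keep it out of the incidence count.

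Most of this stands, and it rules out two stronger conclusions that a reader might infer. One is that a real respiratory signal would be lost; the separate outputs contradict that. The other is that most children would be flagged. That depends on a distribution the documents do not give. At SD 2 it fails in three of the four bands even on an ever-flagged count, and per visit the share stays below half in every band at SD 2 and SD 3.

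The reply does not repair the flag. Mean changes can conceal individual shifts in opposite directions, a listing is not a summary, and the SAP text leaves the status of Low/High open.

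**Conclusion.** The point holds as a defect in one summary. Respiratory rate is the only vital sign in SAP 17.5.1 flagged on a normal range alone. If those flags enter the incidence count, as the section's layout implies, the count mixes stable pre-existing values with new ones and is not comparable with the other rows.

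The loss is one of specificity, confined to this flag. Its size cannot be fixed from the documents: about 4% to 57% ever flagged at SD 2 and 34% to 91% at SD 3, by age band, with correlation 0.5, nine visits and means at the range midpoints. All of these are assumptions except the visit count, which is an upper limit. The missing age rule is a second, smaller gap in the same paragraph.

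**What to change.** - Take Low/High respiratory rate out of the markedly abnormal incidence count, and say so in SAP 17.5.1.
- Present it as a Low/Normal/High shift from baseline, by time point and age category, against both baselines, on the model of SAP 17.3.
- State that age at the visit assigns the band. A child who crosses a band boundary can then change category with an unchanged rate, so mark such children in the listing.
- Keep the change-from-baseline summary and the listing. A child aged 4 who goes from 27 to 35 is High at both times and looks unchanged in a shift table.
- Do not restrict counting to children in range at baseline. That would hide worsening in children already out of range. Baseline 2 may also be the last assessment of the previous study (SAP 6.2), taken after cannabidiol treatment, so an on-drug value could be set aside as pre-existing.

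The cost is SAP wording, one extra descriptive table and fewer flags in the incidence table. No new data are needed.

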17.6. PHYSICAL AND NEUROLOGICAL EXAMINATION

The full physical examination will consist of the following: general appearance, skin, eyes, ears, nose, throat, neck, lymph nodes, chest, heart, abdomen, and extremities. All physical exams will also include an assessment of the subject's height and weight.

A brief neurological examination will consist of the following: mental status, cranial nerves, nystagmus, motor system, sensory system, reflexes, coordination, gait, and station.

The subject's developmental capabilities will be assessed as a part of the neurological examination (in a manner the Investigator sees fit) during the Screening Period (Visit 1) or Visit 2 (Day 1) only, whichever visit occurs first for each respective subject.

Additional examinations may be performed at the discretion of the Investigator.

The following summary will be produced separately for physical and neurological examination:

- Number and percentage of subjects with the results (normal/ANCS/ACS) by time point and age category
- Shifts from baseline according to normal/ANCS/ACS criteria by time point and age category
- Supportive listings will also be provided

17.7. COLUMBIA SUICIDE SEVERITY RATING SCALE (C-SSRS) AND VINELAND ADAPTIVE BEHAVIOR SCALES (VABS)

17.7.2. MISSING DATA METHODS

All data will be evaluated as observed; no imputation method for missing values will be used. A subject who withdraws prior to the last planned observation in a trial period will be included in the analyses up to the time of withdrawal (for any reason). Missing data will result in a reduced sample size for that variable/parameter.

17.7.3. ANALYSIS OF VARIABLES

The qualitative subject status will be summarized as follows:

- Descriptive statistics (n, mean, SD, median, minimum, and maximum) over time and by age category of actual scores and the change from baseline for each quantitative items of VABS
- Number of subjects (and corresponding percentage) per frequency level and per severity scale for each Maladaptive Behavior Critical Items of VABS over time reported by age category
- Number of subjects (and corresponding percentage) over time and by age category per answer (Y/N) for each questions of the C-SSRS "*suicidal ideation*" item
- Number of subjects (and corresponding percentage) over time and by age category per answer (Y/N) for each questions of the C-SSRS "*suicidal behavior*" item

For change from baseline analysis, the two baselines, as defined [Section 6.2](#), will be used in separate tables.

Each of the above items will also be summarized by CBD status for results observed at the Follow-up visit.

Results for each assessment will be listed separately to support these tables.

18. DATA NOT SUMMARIZED OR PRESENTED

The other variables and/or domains not summarized or presented are:

Document: C:\Users\q832483\Documents\Insy CSR\Pending\Ready for QC\New folder\Statistical Analysis Plan.docx
Author: [REDACTED] Version Number: V1.0 Final
Version Date: 04APR2017

Template No: CS_TP_BS016 – Revision 3
Effective Date: 01May2012

Reference: CS_WI_BS005

STATISTICAL ANALYSIS PLAN: PROTOCOL INS011-14-030

Page 34 of 40

• Comments

These domains and/or variables will not be summarized or presented, but will be available in the clinical study database, SDTM and/or ADaM datasets.

Document: C:\Users\q832483\Documents\Insy CSR\Pending\Ready for QC\New folder\Statistical Analysis Plan.docx
Author: [REDACTED] Version Number: V1.0 Final
Version Date: 04APR2017

Template No: CS_TP_BS016 – Revision 3
Effective Date: 01May2012

Reference: CS_WI_BS005

APPENDIX 1. PARTIAL DATE CONVENTIONS

Imputed dates will NOT be presented in the listings.

ALGORITHM FOR TREATMENT EMERGENCE OF ADVERSE EVENTS:

START DATE	STOP DATE	ACTION
Known	Known	If start date < study med start date, then not TEAE If start date >= study med start date, then TEAE
	Partial	If start date < study med start date, then not TEAE If start date >= study med start date, then TEAE
	Missing	If start date < study med start date, then not TEAE If start date >= study med start date, then TEAE
Partial, but known components show that it cannot be on or after study med start date	Known	Not TEAE
	Partial	Not TEAE
	Missing	Not TEAE
Partial, could be on or after study med start date	Known	If stop date < study med start date, then not TEAE If stop date >= study med start date, then TEAE
	Partial	Impute stop date as latest possible date (i.e. last day of month if day unknown or 31st December if day and month are unknown), then: If stop date < study med start date, then not TEAE If stop date >= study med start date, then TEAE
	Missing	Assumed TEAE
Missing	Known	If stop date < study med start date, then not TEAE If stop date >= study med start date, then TEAE

Document: C:\Users\q832483\Documents\Insy CSR\Pending\Ready for QC\New folder\Statistical Analysis Plan.docx
Author: [REDACTED] Version Number: V1.0 Final
Version Date: 04APR2017

Template No: CS_TP_BS016 – Revision 3
Effective Date: 01May2012

Reference: CS_WI_BS005

STATISTICAL ANALYSIS PLAN: PROTOCOL INS011-14-030

Page 37 of 40

START DATE	STOP DATE	ACTION
	Partial	Impute stop date as latest possible date (i.e. last day of month if day unknown or 31st December if day and month are unknown), then: If stop date < study med start date, then not TEAE If stop date >= study med start date, then TEAE
	Missing	Assumed TEAE

ALGORITHM FOR PRIOR / CONCOMITANT MEDICATIONS:

START DATE	STOP DATE	ACTION
Known	Known	If stop date < study med start date, assign as prior If stop date >= study med start date and start date <= end of treatment, assign as concomitant If stop date >= study med start date and start date > end of treatment, assign as post study
	Partial	Impute stop date as latest possible date (i.e. last day of month if day unknown or 31 st December if day and month are unknown), then: If stop date < study med start date, assign as prior If stop date >= study med start date and start date <= end of treatment, assign as concomitant If stop date >= study med start date and start date > end of treatment, assign as post treatment
	Missing	If stop date is missing could never be assumed a prior medication If start date <= end of treatment, assign as concomitant If start date > end of treatment, assign as post treatment
Partial	Known	Impute start date as earliest possible date (i.e. first day of month if day unknown or 1 st January if day and month are unknown), then: If stop date < study med start date, assign as prior If stop date >= study med start date and start date <= end of treatment, assign as concomitant If stop date >= study med start date and start date > end of treatment, assign as post treatment

Document: C:\Users\q832483\Documents\Insy CSR\Pending\Ready for QC\New folder\Statistical Analysis Plan.docx
Author: [REDACTED] Version Number: V1.0 Final
Version Date: 04APR2017

Template No: CS_TP_BS016 – Revision 3
Effective Date: 01May2012

Reference: CS_WI_BS005

STATISTICAL ANALYSIS PLAN: PROTOCOL INS011-14-030

Page 38 of 40

START DATE	STOP DATE	ACTION
	Partial	Impute start date as earliest possible date (i.e. first day of month if day unknown or 1 st January if day and month are unknown) and impute stop date as latest possible date (i.e. last day of month if day unknown or 31 st December if day and month are unknown), then: If stop date < study med start date, assign as prior If stop date >= study med start date and start date <= end of treatment, assign as concomitant If stop date >= study med start date and start date > end of treatment, assign as post treatment
	Missing	Impute start date as earliest possible date (i.e. first day of month if day unknown or 1 st January if day and month are unknown), then: If stop date is missing could never be assumed a prior medication If start date <= end of treatment, assign as concomitant If start date > end of treatment, assign as post treatment
Missing	Known	If stop date < study med start date, assign as prior If stop date >= study med start date, assign as concomitant Cannot be assigned as 'post treatment'
	Partial	Impute stop date as latest possible date (i.e. last day of month if day unknown or 31 st December if day and month are unknown), then: If stop date < study med start date, assign as prior If stop date >= study med start date, assign as concomitant Cannot be assigned as 'post treatment'
	Missing	Assign as concomitant

Document: C:\Users\q832483\Documents\Insy CSR\Pending\Ready for QC\New folder\Statistical Analysis Plan.docx
Author: [REDACTED] Version Number: V1.0 Final
Version Date: 04APR2017

Template No: CS_TP_BS016 – Revision 3
Effective Date: 01May2012

Reference: CS_WI_BS005

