Data listings and univariate descriptive summary statistics (number and percentages) will be generated for TEAEs and SAEs. The AEs with missing onset dates or AEs with missing onset times occurring on the same day as the administration of investigational product will be summarized as TEAEs. Both AEs and SAEs will be summarized using the Medical Dictionary for Regulatory Activities (MedDRA). Each verbatim term will be mapped to a lower level term, then to a preferred term (PT), and finally to a system organ class (SOC). The number and percentage of subjects with ≥ 1 TEAE for each SOC and preferred term will be summarized.

Laboratory analytes will be summarized as mean change from baseline to endpoint. Shift tables will also be produced describing changes from normal to abnormal (high and low) levels or abnormal (high and low) to normal levels.

For each continuous endpoint, descriptive statistics (number, mean, median, minimum, maximum, standard deviation [SD], and 95% confidence interval [CI]) will be generated. This analysis will be carried out for the change from baseline in frequency, severity, and duration of seizures, IPES, VABS, and C-SSRS scores, as well as parent(s)/caregiver(s) and Investigator CGI-I and CGI-S. Subjects enrolled from INS011-15-054 will be excluded from IPES, VABS, and C-SSRS scores evaluation.

Concentrations of cannabidiol and its 7-OH metabolite will be measured at each visit except Visits 3 and 4. A descriptive summary of observed blood concentrations (number, mean, median, SD, minimum value, and maximum value) will be displayed.

TABLE OF CONTENTS

APPROVAL SIGNATURES	2
Synopsis	3
Table of contents	8
LIST OF ABBREVIATIONS AND DEFINITIONS OF TERMS	13
1.0 INTRODUCTION	16
1.1 Cannabidiol	16
1.1.1 Mechanism of Action	16
1.1.2 Metabolism and Potential Drug Interactions.....	17
1.1.3 Nonclinical	18
1.1.3.1 Safety.....	18
1.1.3.2 Efficacy in Epilepsy Animal Models	19
1.1.4 Clinical	19
1.1.4.1 Pharmacokinetics.....	19
1.1.4.2 Overview of Safety.....	19
1.1.4.3 Efficacy in Human Epilepsy.....	21
1.1.5 Previous Studies with the Investigational Product	21
1.2 Pediatric Treatment-Resistant Seizure Disorders	22
1.2.1 Lennox-Gastaut Syndrome.....	23
1.2.2 Dravet Syndrome.....	24
1.2.3 Study Population	24
1.3 Study Rationale.....	25
1.4 Risk-Benefit Analysis.....	25
1.5 Compliance	26
2.0 STUDY OBJECTIVES	27
2.1 Objectives	27
3.0 INVESTIGATIONAL PLAN	28
3.1 Summary of Study Design.....	28
3.2 Medical and Safety Data Review	30

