5.2 Treatment Period

Subjects that completed INS011-14-029 will complete this study through the 48 week visit, unless they are discontinued due to a reason described in Section 3.4.3, or until the investigational product is successfully approved for marketing in the US (whichever occurs earlier). For subjects that participated in INS011-15-054 will participate through the Week 48 visit unless they are discontinued due to a reason described in Section 3.4.3, or until the investigational product is successfully approved for marketing in the US (whichever occurs earlier); however, the combined treatment duration in INS011-14-030 and INS011-15-054 will not exceed approximately 48 weeks

At Visits 2, 8, and 9, all assessments are to precede administration of the morning dose of the investigational product. Specifically, the subject will NOT receive the investigational product on the morning of Visits 2, 8, and 9 UNTIL all assessments have been completed. The morning dose of the investigational product should be administered following completion of all assessments.

Given the timing of study assessments in regards to administration of the investigational product and the twice daily dosing of this medication, all visits requiring in-clinic dose administration will preferably be scheduled in the morning. Ideally, all assessments should be completed before 12 PM (noon) in the time zone of the study center to adhere as closely as possible to the 12-hour interval for dosing (see Section 4.6).

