6.1.4 Clinical Laboratory Evaluations

All clinical laboratory tests will be reviewed for results of potential clinical significance throughout the study. The Investigator will evaluate any change in laboratory values. If the Investigator determines a laboratory abnormality to be clinically significant, it is considered a laboratory AE; however, if the abnormal laboratory value is consistent with a current diagnosis, it may be documented accordingly.

The following laboratory tests will be assessed at the time points specified by Table 1.

- Hematology: complete blood count (CBC) with differential, including platelet count, neutrophils, lymphocytes, eosinophils, basophils, monocytes, hemoglobin, and hematocrit
- Serum chemistry: total protein, albumin, creatinine, blood urea nitrogen (BUN), uric acid, total bilirubin, direct bilirubin, alkaline phosphatase, FSH, AST, ALT, glucose, calcium, phosphorus, bicarbonate, chloride, sodium, and potassium
- Urinalysis: specific gravity, pH, color, and presence of white blood cells (WBCs), red blood cells (RBCs), and proteins
- β -hCG in urine (pregnancy test)

LFTs (e.g., albumin, direct and total bilirubin, AST, and ALT) will be closely monitored to identify any damage that could be induced by the investigational product.

Levels of FSH will be monitored as a potential surrogate outcome for gametocyte damage.

Laboratory values outside the reference limits suspected to be of any clinical significance will be repeated. Subjects in whom suspected clinical significance is confirmed will either not be included or if already enrolled will be followed until normalization or for as long as the Investigator considers necessary. Additional laboratory variables may be performed for safety reasons if judged appropriate by the Investigator. Further details are provided in the Laboratory Manual.

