8.3.4.1 AEs

The TEAEs are defined as AEs that first occur or worsen in severity after the first administration of the investigational product. Such AEs will be coded using the MedDRA coding dictionary and will be summarized by presenting the number and percentage of subjects having any AE, having an AE in each SOC, and having each individual AE as reported by PT. Furthermore, a summary for SAEs and summaries by severity and relationship to the investigational product will be presented by dose and overall. The most frequent (5%) AEs and drug related AEs will also be provided.

All percentages will be based on the number of subjects in the Safety Population.

In the summaries, AEs will be counted only once per subject. If a subject reports the same AE more than once, it will be counted with its worst severity and closest relationship to investigational product. Only those AEs that begin between start and end of study will be summarized.

The AEs will also be listed by subject and dose.

Subject death due to any cause and subjects with AEs leading to investigational product discontinuation will be listed and summarized by dose and overall.

The proportion of subjects that discontinue investigational product or experience dose interruption due to treatment emergent AEs will be summarized by dose and for all subjects.

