6.2. BASELINE

For this study, subjects will have 2 different baselines defined as follows:

- The first one (Baseline 1) will be the same as that defined in their previous study. This baseline was defined in the 029 as “baseline is defined as the last non-missing measurement taken prior to reference start date (including unscheduled assessments). In the case where the last non-missing measurement and the reference start date coincide, that measurement will be considered prior to baseline. However, AEs and medications commencing on the reference start date will be considered post baseline, unless the start time of the AE is known to be prior to the first dosing of the study medication.”
- The second one (Baseline 2) will be the intra-study baseline, defined as the last non-missing measurement prior to the first dose including pre-dose assessments performed on the reference start date. The intra-study baseline could correspond to:
 - Last assessment from the previous study (e.g. Day 11 for subjects from INS011-14-029)
 - Screening (Visit 1) assessment of INS011-14-030
 - Data collected at Day 1 (Visit 2) of INS011-14-030

Document: C:\Users\q832483\Documents\Insy CSR\Pending\Ready for QC\New folder\Statistical Analysis Plan.docx
Author: [REDACTED] Version Number: V1.0 Final
Version Date: 04APR2017

Template No: CS_TP_BS016 – Revision 3
Effective Date: 01May2012

Reference: CS_WI_BS005

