17.1. ADVERSE EVENTS

Adverse Events (AEs) will be coded using the latest version of MedDRA central coding dictionary.

Treatment emergent adverse events (TEAEs) are defined as AEs that first occur or worsen in severity after the first administration of the study medication.

See [Appendix 1](#) for handling of partial dates for AEs. In the case where it is not possible to define an AE as treatment emergent or not, the AE will be classified by the worst case; i.e. treatment emergent.

An overall summary of number of subjects within each of the categories described in the sub-section below, will be provided as specified in the templates. In the summaries, AEs will be counted only once per subject. Only those AEs that begin between start and end of study will be summarized.

Each summary described in Adverse Event section (except [Section 17.1.2](#) and [Section 17.1.3](#)) will be repeated for TEAEs observed during the Follow-up period and presented by CBD status.

Listings will include TEAEs and Non-TEAEs.

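### SAP Appendix 1 compares dates only, so an adverse event with a known pre-dose onset time on Day 1 is classed as treatment-emergent, against the plan's own definition

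*SAP*

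**What the plan says.** SAP Section 17.1 defines TEAEs as "AEs that first occur or worsen in severity after the first administration of the study medication". Protocol Section 8.3.4.1 gives the same definition. SAP 17.1 also has a worst-case default to TEAE, but limits it to AEs that cannot be classified: "In the case where it is not possible to define an AE as treatment emergent or not".

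The protocol synopsis, under statistical methods, covers the day of dosing: "AEs with missing onset times occurring on the same day as the administration of investigational product will be summarized as TEAEs". SAP Section 6.2 quotes a rule from study INS011-14-029, under Baseline 1, by which AEs starting on the reference start date count as post-baseline "unless the start time of the AE is known to be prior to the first dosing of the study medication". Baseline 2, the intra-study baseline, does not repeat that exception.

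SAP Appendix 1 is the algorithm that will be programmed. Where the start date is known it reads "If start date >= study med start date, then TEAE", and the rule is the same whether the stop date is known, partial or missing.

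On the timing of Visit 2, protocol Section 5.2 states: "At Visits 2, 8, and 9, all assessments are to precede administration of the morning dose of the investigational product". On laboratory findings, protocol Section 6.1.4 states: "If the Investigator determines a laboratory abnormality to be clinically significant, it is considered a laboratory AE". Section 6.1.5 treats clinically significant vital-sign, examination and other safety findings likewise.

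**The concern.** Day 1 is the date on which a date comparison and an after-the-dose definition can part company. In this study AEs are recorded at Visit 2, and the assessments there come before the dose. An event or finding can therefore carry a Day 1 date and a pre-dose time. Vital signs must be taken at Visit 2 whatever was done earlier (protocol Section 5.2.1), so at least one source of such findings is always present.

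The incidence and severity of TEAEs is the primary criterion of the study. If Appendix 1 is programmed as written, the tables can include events that the SAP's own definition excludes. The same finding can also be the subject's Baseline 2 value, because Section 6.2 admits pre-dose measurements from the first-dose day. It would then be a TEAE in one table and the baseline in another.

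Protocol Section 8.2.1 lets the SAP change methods if the change is documented. SAP Section 3.3, which lists changes from the protocol, does not mention this one.

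**Working it through.** The plan states no figure on this point, so there is none to reproduce. The check compares the two rules case by case and then works out what one subject is worth.

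**Step 1. The two rules.**
- Rule A (Appendix 1, known start date): TEAE if the start date is on or after the first-dose date.
- Rule B (SAP 17.1 and protocol 8.3.4.1, with the synopsis rule for missing times): TEAE if onset follows the first dose; a Day 1 AE with no onset time defaults to TEAE.

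**Step 2. Case by case.** The 10:00 dose on Day 1 is assumed for illustration.

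| AE onset | Rule A | Rule B |
|---|---|---|
| Day -1 | not TEAE | not TEAE |
| Day 1, 08:00 (before dose) | **TEAE** | **not TEAE** |
| Day 1, time missing | TEAE | TEAE |
| Day 1, 14:00 (after dose) | TEAE | TEAE |
| Day 2 | TEAE | TEAE |

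Only the second row differs. The worst-case default in SAP 17.1 does not cover it, because an AE with a known pre-dose time can be classified.

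**Step 3. What one subject is worth.** AEs are counted once per subject, so a table row changes only if the subject has no other qualifying event in that row. One such subject adds 100/N percentage points. SAP 17.1.1 also calls for a table of TEAEs in at least 5% of subjects; that cut-off is 0.05 × N subjects.

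| N | Source of N | One subject (points) | 5% cut-off (subjects) |
|---|---|---|---|
| 80 | protocol maximum | 100/80 = 1.25 | 4 |
| 60 | maximum from INS011-14-029 | 100/60 = 1.67 | 3 |
| 40 | assumed | 100/40 = 2.50 | 2 |
| 20 | maximum from INS011-15-054 | 100/20 = 5.00 | 1 |

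The documents do not give the size of any age category. The smaller values of N show how the effect grows in the by-age columns.

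**Step 4. How many subjects.** The documents give no count of AEs with a known pre-dose onset on Day 1, and nothing from which to derive one.

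**The case against.** The best defence is that the disputed case will be rare and the error is harmless.

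- **Few findings reach it.** Except for vital signs, Visit 2 assessments may be carried over from the previous 14 days (Table 1, footnote c; Section 5.2.1). A finding becomes an AE only if judged clinically significant, and one consistent with a current diagnosis may be documented as such instead. Entry requires medical stability and excludes clinically significant laboratory values from the past 14 days, unless the investigator accepts them.
- **The direction is conservative.** The rule adds TEAEs and removes none. The analysis is descriptive, and the listings show TEAEs and non-TEAEs.
- **The onset time may not exist.** Protocol Section 6.1.2 names only the date of onset among the AE details. If no time is collected, the synopsis rule makes every Day 1 AE a TEAE, exactly as Appendix 1 does.
- **The baseline conflict is partial.** The SAP also reports change from Baseline 1, in the previous study, where a finding new on Day 1 can show as a change. Only the Baseline 2 tables would show none.
- **These subjects may already be on drug.** After rollover without a gap, a pre-dose Day 1 event is not a drug-free event.

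These points stand and limit the size. They do not reconcile the texts: the definition, the synopsis and Appendix 1 still give different answers for a Day 1 AE with a known pre-dose time. Prior exposure does not settle it either, because study day and treatment emergence are counted from the first dose in this study.

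A reader might also infer that events are counted twice when Visit 2 coincides with Day 11 of INS011-14-029. The documents do not show this. It depends on that study's AE cut-off, which they do not give, and Section 5.2.1 deliberately uses the shared visit's data in both analyses.

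**Conclusion.** The inconsistency is real and narrow. Appendix 1 misclassifies one case, an AE with a known start time on Day 1 before the first extension dose. The error inflates TEAE incidence and is probably small. Its firm measure is 1.25 percentage points per subject counted only because of it at N = 80, and more within an age category. It arises only if onset times are recorded.

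Two stronger readings are tempting. One is that findings forming the extension baseline are counted as TEAEs as a matter of course. They are not: the finding must be judged clinically significant, recorded as an AE, and dated Day 1 with a pre-dose time.

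The other is that the visit schedule shows what share of TEAEs is wrong. Without a Screening Visit, one of two scheduled ECGs falls on Day 1. So does one of five laboratory panels in Table 1 (Day 1, Weeks 24, 36 and 48, Follow-up), or one of seven if the Week 4 and Week 8 panels in Section 5.2.3 are added. These fractions count visits, not events. Using them as error rates assumes an equal chance of a significant finding at every visit, which conflicts with the entry criteria and ignores carry-over.

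**What to change.** Replace the rule in each of the three known-start-date rows of Appendix 1 for dates on or after the first dose:

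- Start date later than the first-dose date: TEAE.
- Start date equal to the first-dose date: not TEAE if the onset time is recorded and precedes the first dose, unless the AE worsens in severity after that dose. Otherwise (onset after the dose, or time missing): TEAE.

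The worsening clause is needed because SAP 17.1 counts worsening after the first dose. Do not add a blanket exclusion for findings of Visit 2 assessments. It would override the synopsis rule for missing times, and it would need a link from each AE to an assessment that the documents do not describe.

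Confirm first that the eCRF records AE onset time; the synopsis implies it, but protocol Section 6.1.2 does not name it. Dose administration times are already due to be listed under SAP Section 14. Keep pre-dose events in the listings.

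The cost is a wording change and a small addition to the programming. The downside is slightly fewer Day 1 TEAEs.
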